3.2 Exposure assessment

Dietary information of the cohort was ascertained by a self-administered 217-item food frequency questionnaire (FFQ) [1]. The FFQ was validated by comparison with 4-d weighed food diaries and a repeated FFQ on 283 women three years after baseline [1].

The baseline questionnaire asked if participants identify as a meat-eater, vegetarian, or vegan – this will constitute the self-identified dietary group variable. It also included questions about consumption of foods and beverages in the form of ‘how often do you eat [specific food or beverage]?’ or similar. Ten responses were possible: 0 ‘never’, 1 ‘< once per month’, 2 ‘1-3 per month’, 3 ‘once per week’, 4 ‘2-4 per week’, 5 ‘5-6 per week’, 6 ‘once per day’, 7 ‘2-3 per day’, 8 ‘4-5 per day’, or 9 ‘6+ per day’. We will convert the responses to these questions into daily-based consumption frequencies as follows: 0, 0.02, 0.07, 0.14, 0.4, 0.8, 1, 2.5, 4.5, 6 times per day. Each exposure variable of interest will then be calculated in servings per day by summing daily consumptions of relevant items. For example, we will sum daily consumptions of unprocessed beef, pork, and lamb into one group titled ‘red meat’; questions on unprocessed chicken or turkey into ‘unprocessed poultry’; and questions around processed red or white meat or poultry into ‘processed meat’. Red meat, unprocessed poultry, and processed meat will be summed to form ‘total meat’. Similarly, questions on fish intake will be summed to calculate oily fish, non-oily fish, and total fish intakes; and questions on intake of dairy products will be summed to calculate milk, yogurt, cheese, cream, dairy desserts, and total dairy intakes in servings per day. Meat, fish, eggs and dairy exposures will then be used to classify subjects as regular meat-eaters, occasional meat-eaters, pescatarians, vegetarians, or vegans (Table 1). Due to the small number of vegans, vegetarians and vegans will be combined in the main analysis and considered separately in sensitivity analyses.

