To explore potential associations between foods and beverages and hip fracture incidence, food and beverage intake variables in grams per day will be calculated by multiplying servings per day intake variables by standard portion weights, and summing relevant FFQ items. Food and beverage intake variables (grams/day) will be used to explore the effects of increment increases in intake on hip fracture risk, and to categorise participants into non-consumers (if > 1000 participants in this category) and levels of intake for all exposure variables, ensuring equal distribution of the population size among categories where possible. For intakes of milk, tea, coffee, and tea and coffee combined, increment increases and categories of intake will be defined by glasses and cups per day using standard sizes with the lowest exposure category as the reference group. For fruits, vegetables, and fruits and vegetables combined, categories will be defined to compare intakes below and above the

recommended five-a-day (400 g/day) intake, which will be used as the reference category. All other food and beverage exposures will be split into thirds or quarters.

Nutrient variables will be derived by multiplying food and beverage intakes (g/day) by nutrient concentrations in each food or beverage item using McCance and Widdowson’s Food Composition database (5th edition) [2].

4. Outcomes

Participants will be followed up via record linkage to the NHS Hospital Episode Statistics up to 31 March 2019. The primary outcome will be hip fracture incidence (International Classification of Diseases, ICD-9 code 820, and ICD-10 codes S72-S72.2). Hip fracture cases will also be identified by hip replacements (ICD-10 code Z96.64). The timeframe will be person years until hip fracture incidence (or until end of study period or death in those without a hip fracture), calculated as age at time of event (or non-event) minus age at study entry.

5. Sample size

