7.3 Sensitivity analyses

For the dietary group analysis, we will present models with vegans and vegetarians separated. We will also compare risk estimates between self-identified and data-derived dietary groups. For all analyses, we will explore the potential mediating effect of covariates identified in DAG models as being associated with hip fracture incidence and plausibly caused by the exposure by adding each of these covariates to adjusted models independently. Models will be presented with and without adjustment for BMI. To reduce risk of bias due to changes in exposure over time, phase two dietary data (collected four years after baseline) will be compared with baseline dietary data. In cases of substantial exposure change over time (e.g., > 10% of participants changing their dietary group or primary exposure categories), models will be repeated using phase two data if there is sufficient power.

Additional sensitivity analyses will involve excluding cases occurring in the first five years of follow-up (to check for reverse causality), and excluding participants on long-term treatment for illnesses. All analyses will be performed using Stata. Two-sided p values < 0.05 will be considered statistically significant. We acknowledge that the large number of planned exposure-outcome association tests increases the risk of a type-2 error. However, the alpha value will not be restricted below $p < 0.05$ since secondary analyses (including most nutrient-hip fracture associations) will be exploratory, with only the primary analyses considered hypothesis-testing. All analyses performed and effect sizes computed will be presented in resulting manuscripts to avoid bias in selection of the reported result.

8. Missing data

Participants with missing data for an FFQ item will be considered non-consumers. Participants will be excluded from each specific analysis if they have missing data for any other variable required in that analysis. Techniques to impute missing dietary or covariate data will not be performed.

9. Timescales

Target analysis completion date (excluding manuscript preparations): Jan 2021.

10. References

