Vegetables (cat)	Categorise vegetables (con) as: 0 – 160 g, > 160 – 240 g, > 240 – 320 g, > 320 – 400 g, and > 400 g
Vegetables (con)	Convert all specific vegetable intake variables to servings/day then multiply by a standard portion weight to give g/day of each specific vegetable, then sum to give g/day of total vegetable intake
Fruits and vegetables (cat)	Categorise fruits and vegetables (con) as: 0 – 240 g, > 240 – 400 g, > 400 – 560 g, > 560 – 720 g, > 720 g
Fruits and vegetables (con)	Sum fruits (g/day) and vegetables (g/day)
2. Animal products	
Total animal products (cat)	Categorise total animal products (con) into non-consumers and quartiles of intake
Total animal products (con)	Sum total meat, total fish, eggs, and total dairy (all in g/day)
Total meat (cat)	Categorise total meat (con) into non-consumers and quartiles of intake
Total meat (con)	Sum red meat, processed meat, and unprocessed poultry (all in g/day)
Red meat (cat)	Categorise red meat (con) into non-consumers and quartiles of intake
Red meat (con)	Convert beef, pork and lamb variables to servings/day, multiply each by standard portion weights to give g/day of each variable, then sum to give g/day of total red meat intake

Processed meat (cat)	Categorise processed meat (con) into non-consumers and quartiles of intake
Processed meat (con)	Convert all processed meat variables (including processed poultry) to servings/day, multiply each by standard portion weights to give g/day of each variable, then sum to give g/day of total processed meat intake
Unprocessed poultry (cat)	Categorise unprocessed poultry (con) into non-consumers and quartiles of intake
Unprocessed poultry (con)	Convert unprocessed poultry variables (chicken and turkey) to servings/day, multiply each by standard portion weights to give g/day of each variable, then sum to give g/day of total unprocessed poultry intake
Total fish (cat)	Categorise total fish (con) into non-consumers and quartiles of intake
Total fish (con)	Sum oily and non-oily fish intakes (g/day)
Oily fish (cat)	Categorise oily fish (con) into non-consumers and quartiles of intake
Oily fish (con)	Convert oily fish variables to servings/day, multiply each by standard portion weights to give g/day of each variable, then sum to give g/day of total oily fish intake
Non-oily fish (cat)	Categorise non-oily fish (con) into non-consumers and quartiles of intake

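### The 10% category-change trigger in SAP section 7.3 does not separate diet change from measurement error for banded intakes, and the phase two refit has no baseline-diet comparator in the same women

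*SAP*

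**What the plan says.** Baseline diet comes from one food frequency questionnaire (FFQ; section 3.2) and is related to hip fractures recorded "up to 31 March 2019" (section 4).

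Section 7.3 sets out the step against change in exposure: "phase two dietary data (collected four years after baseline) will be compared with baseline dietary data". The rule that follows is "In cases of substantial exposure change over time (e.g., > 10% of participants changing their dietary group or primary exposure categories), models will be repeated", and the action in full is that "models will be repeated using phase two data if there is sufficient power". The 10% is given as an example, and the power condition has no threshold.

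Categories are mostly fine cuts. Section 3.2 divides most foods into thirds or quarters. Supplementary Table 1 uses five fixed bands for fruits and vegetables, and elsewhere rules such as "Categorise total meat (con) into non-consumers and quartiles of intake".

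Sections 7.2.1 and 7.2.2 show that phase two data exist for only some of the women. The number is not given, and section 7.3 does not name the phase two instrument. The SAP mentions "a repeated FFQ on 283 women three years after baseline" as part of FFQ validation, but reports no correlation or agreement figure and does not use this sample to separate error from change.

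Nothing else in the SAP addresses diet change. The exclusion of cases in the first five years is stated to be for reverse causality.

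**The concern.** Two parts of the step do not do what they are meant to do.

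- **The trigger.** Two imperfect measurements of an unchanged diet will place many women in different categories. The finer the cuts, the more women move. A fixed switching percentage therefore reflects repeatability and number of categories as much as real change, and a report could describe measurement error as substantial dietary change.
- **The comparison.** If the phase two model is set beside the full-cohort baseline model, the two differ in women included, in when diet was measured, probably in start of follow-up, and in power. A difference in hazard ratios would have several explanations, of which diet change is only one.

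The undefined power condition adds a third weakness: whether the check is run at all is left to a judgement that the plan does not fix in advance.

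At stake is the usefulness of the plan's one safeguard against a bias that it names itself. The main analyses are not altered.

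**Working it through.** **1. The plan's own power figure, to fix the event count.** Section 5 assumes 26,300 women and 3% incidence, so 26,300 × 0.03 = 789 events. Table 2 gives SD 0.36 for dietary group and a minimum detectable HR of 1.32. With two-sided 0.05 and 80% power:

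HR = exp[(1.960 + 0.842) / (0.36 × √789)] = exp[2.802 / 10.11] = 1.319

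This reproduces 1.32; power at HR 1.32 is 80.2%.

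**2. Category switching with no true diet change.** Assumptions: two measurements, bivariate normal, same distribution at both times, correlation r arising from error alone. The SAP gives no r, so a range is shown. The proportion switching is 1 − Σ P(both measurements fall in category j).

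| r | Thirds | Quarters | Fifths |
|---|---|---|---|
| 0.5 | 51% | 61% | 68% |
| 0.6 | 47% | 57% | 64% |
| 0.7 | 42% | 52% | 60% |
| 0.8 | 35% | 46% | 53% |
| 0.9 | 26% | 35% | 43% |
| 0.95 | 18% | 26% | 33% |

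Switching falls to 10% only at r of about 0.985 (thirds), 0.993 (quarters) or 0.996 (fifths).

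The SAP's own fruit and vegetable bands (cuts at 240, 400, 560 and 720 g), with the Table 2 SD of 300 g and an assumed mean of 500 to 900 g, give 22% to 43% at r = 0.9. With 10% of women assumed to be non-consumers and the rest in quartiles, the figure at r = 0.9 is 41%. Both treat the underlying intake as normal.

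**3. The same switching rate from two different causes.** Quarter switching is 52% with no true change and reliability 0.70. It is also 52% with reliability 0.90 and a true-diet correlation of 0.78 between the two times. In both cases the observed correlation is about 0.70 (0.90 × 0.78 = 0.70). The switching rate alone cannot tell them apart.

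**4. Dietary group.** Here the result depends on further assumptions. Counting only moves across the regular/occasional meat cut-off, with all other groups held stable, 60% to 85% of women assumed to eat meat and 50% to 80% of those assumed regular:

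- r = 0.7: 10.5% to 21.5%
- r = 0.8: 8.5% to 17.4%
- r = 0.9: 6.0% to 12.2%

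These ranges straddle 10% at r of 0.8 to 0.9.

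**5. Power in the phase two subset.** The number of phase two women is not given, so the share of the 789 events is assumed. Minimum detectable HR = exp[2.802 / (0.36 × √events)]; power at HR 1.32 = Φ(0.36 × √events × ln 1.32 − 1.960).

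| Share of events | Events | Minimum detectable HR | Power at HR 1.32 |
|---|---|---|---|
| 25% | 197 | 1.74 | 29% |
| 40% | 316 | 1.55 | 43% |
| 50% | 394 | 1.48 | 51% |
| 75% | 592 | 1.38 | 68% |

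If sufficient power meant the 80% of section 5 at the same HR, none of these shares would meet it and the check would not be run for dietary group.

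**The case against.** The strongest reply is that an easily met trigger does little harm: it means that the sensitivity model is run. That largely stands. The 10% is also only an example, and section 7.3 commits to presenting all analyses performed. What remains is that crossing 10% cannot be reported as evidence of change, and that the power condition can still stop the check.

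Several stronger readings are tempting, and the documents do not support them:

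- **That error is shown to exceed 10% for every exposure.** The SAP gives no repeatability figure. The conclusion is safe for thirds, quarters and five bands over any plausible range, but not for dietary group.
- **That one FFQ is swapped for another in different women.** The phase two instrument is not named, the 283-woman repeat at three years is the validation exercise, and phase two women are a subset of the same cohort.
- **That the check shows nothing, or that null results become uninterpretable.** If diets changed, phase two diet is closer in time to later fractures and its hazard ratio can differ, so agreement gives some reassurance. Equal attenuation of both models holds only with equal error and no true change. Reliance on one main diet measurement is a limitation of many cohorts and is not in itself an error in this plan.
- **That follow-up is of a known long duration.** The SAP gives an end date but no recruitment dates.

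**Conclusion.** The concern holds for banded foods and nutrients. With no true change, 26% to 68% of women would switch among thirds, quarters or fifths at r from 0.9 down to 0.5, so the 10% rule does not identify real change. This rests on an assumed r and a bivariate normal model, but the gap to 10% is wide enough that neither is critical. For dietary group it is not established.

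The more important fault is the missing comparator. Without a baseline-diet model in the same women from the same start, a difference from the main result cannot be attributed to diet change. This follows from the text of section 7.3 and needs no assumption about r.

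Severity is minor to moderate: one sensitivity analysis is affected, but it is the only one directed at this bias.

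**What to change.** In section 7.3, remove the 10% trigger and the undefined power condition, and state that the following will be done in all cases.

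1. Take women with phase two dietary data who are free of hip fracture at phase two, and start follow-up at the phase two date. Averaging from baseline would use diet measured after follow-up began.
2. In these women fit (a) baseline diet and (b) phase two diet. For continuous intakes, optionally add (c) the mean of the two.
3. Compare these models with each other and not with the full-cohort model.
4. For dietary group, report baseline group and phase two group in the same women. Label any analysis of women in the same group at both times as a further restriction, since it changes the sample again.
5. Report the baseline to phase two correlation or agreement for each primary exposure, and name the phase two instrument. A remaining difference between (a) and (b) can still reflect error as well as change, and these figures help the reader to judge it.

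As an illustration of (c): with classical error, equal reliability, no true change and one mismeasured exposure, a single measurement keeps a share r of the log hazard ratio and the mean of two keeps 2r/(1+r). That is 60% versus 75% at r = 0.6, and 70% versus 82% at r = 0.7. The mutual adjustment in section 7.1.1 means that these figures need not apply here, which is why (c) is optional.

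The cost is SAP wording and a few more models on phase two data that the plan already intends to use. The downside is precision in a subset, so the models should remain sensitivity analyses, read by estimates and intervals and not by significance.

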2.1 Exclusion criteria

Participants will be excluded from analyses for any of the following reasons:

- Not a resident of England
- Unable to link dietary and lifestyle data with hospital episode data (e.g. no NHS number provided and unable to match with records)
- Unreliable or missing nutrient or covariate data (e.g., $\geq 20\%$ of food frequencies missing)
- Had a hip fracture or osteoporosis before or on the date of recruitment

3. Exposures

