7.1.1 Accounting for confounding

For all primary analyses, we will present age-adjusted, minimally adjusted, and fully adjusted models. Minimally adjusted models will be adjusted for the minimally sufficient set of confounders. Three directed acyclic graphs (DAGs) will be constructed using the online tool DAGitty, and following

available guidelines on the creation and reporting of DAG models to determine minimal adjustment sets in models of associations between hip fracture and 1) dietary patterns; 2) foods and beverages; and 3) nutrient intakes [7]. Confounders will be considered as covariates that are 1) risk factors of the outcome; 2) associated with the exposure; and 3) not caused by the exposure [8]. Confounders common to all research questions will likely include: age at baseline, ethnicity, socio-economic status, education, marriage, physical activity, smoking, alcohol, BMI (or height and weight), number of children, menopausal status, chronic disease at baseline, and fracture at baseline (non-hip). A list of likely confounders and their derivation is summarised in Supplementary Table 2. We will adjust for baseline chronic disease and fracture prevalence at sites besides the hip rather than excluding these subjects in minimally adjusted models to reduce the risk of selection bias that would result from excluding unhealthier subjects. Fully adjusted models will be further adjusted for competing exposures.

Energy intake will be adjusted for using the ‘all-components’ method for all analyses except dietary groups, for which energy intake could plausibly be a mediator, thus will remain unadjusted [9]. This method involves adjusting for all other individual components of energy intake besides the exposure at hand, and has been shown to produce the least biased and most precise estimand for relative and total causal effects [9]. For food and beverage exposures of interest, this will involve mutual adjustment for other major foods and beverages or food and beverage groups that might be associated with hip fracture incidence. For energy-contributing nutrient exposures of interest (macronutrients), this will involve mutual adjustment for other energy-contributing nutrients (e.g., saturated and unsaturated fat). For non-energy contributing nutrient exposures (micronutrients), this will involve adjustment for all energy-contributing nutrients, whilst avoiding over-adjustment as a result of high correlation between nutrients.

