7.2 Subgroup analyses

7.2.1 Dietary group

We will stratify all models by age (<60, > 60), BMI (<23.5, >23.5), SES (routine/manual, intermediate, professional/managerial), education (\geq A level, \leq O level), smoking status (current, former/never), alcohol consumption (< 1/week, \geq 1/week), menopausal status (pre, post), physical activity levels (inactive/low, moderate/high), and use of dietary supplements (yes/no) to determine their roles as potential effect modifiers. Effect modifiers will be defined as any covariate that meets the criteria for a confounder (previously defined) and could plausibly modify the association at varying levels of that covariate. Potential effect modifiers will also be added to all models as interaction terms. Models stratified by calcium, vitamin D, and vitamin B12 supplement use will be presented in those with phase 2 questionnaire data only, since this was not collected at baseline.

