7.2.2 Foods, beverages and nutrients

We will fit additional Cox models for types of meat (unprocessed red, all processed, and unprocessed poultry), fish (oily and non-oily), dairy (milk, yoghurt, cheese, cream, and dairy desserts), and coffee (caffeinated and decaffeinated) intakes, treating each exposure intake as both categorical and continuous.

We will stratify models for combined fruits and vegetables consumption, combined tea and coffee consumption, and protein, calcium, and vitamin D intakes by age, BMI, menopausal status, and use of dietary supplements to determine their roles as potential effect modifiers, and will add these variables to fully adjusted models as interaction terms. The same cut-off points will be used as in the vegetarian diets analysis (section 3.2). The effect of protein intake on hip fracture will be further stratified by physical activity and calcium intake. We will also present models for all dietary exposures stratified by calcium and vitamin D supplement use in those with phase 2 questionnaire data only.

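### Models that use phase 2 diet or supplement data keep the clock running from study entry, so a hip fracture before phase 2 counts as an event for an exposure or stratum recorded after it

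*SAP*

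**What the plan says.** Section 4 gives the only definition of person-time in the SAP: "calculated as age at time of event (or non-event) minus age at study entry". Section 2.1 sets the only exclusion for prevalent disease: "Had a hip fracture or osteoporosis before or on the date of recruitment".

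Three later sections bring in information from the phase 2 questionnaire:

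- Section 7.3 compares baseline diet with "phase two dietary data (collected four years after baseline"). If change is substantial (more than 10% of women changing group or category is the example given), "models will be repeated using phase two data if there is sufficient power".
- Section 7.2.1 stratifies the dietary-group models by calcium, vitamin D and vitamin B12 supplement use. These models "will be presented in those with phase 2 questionnaire data only, since this was not collected at baseline".
- Section 7.2.2 presents the models for all dietary exposures "stratified by calcium and vitamin D supplement use in those with phase 2 questionnaire data only".

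None of these sections moves the start of follow-up, introduces delayed entry or shifts the fracture exclusion to the phase 2 date. Section 7.3 separately lists "excluding cases occurring in the first five years of follow-up (to check for reverse causality") among its additional sensitivity analyses.

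**The concern.** Take a woman who breaks her hip in year 2 and answers phase 2 in year 4. Under the section 4 clock she is an event at year 2. In a repeat model, the diet credited with that event is the diet she reported two years after it. In a supplement-stratified model, the stratum she sits in may be one she joined because of the fracture.

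The repeat models exist to reduce bias from changing exposure. If women change diet after a fracture, these models would add reverse causation instead. In the supplement strata the exposure is still baseline diet, so the danger there is a false interaction. It arises when the relative change in supplement use after a fracture differs between diet groups, either because uptake differs or because use otherwise differs.

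**Working it through.** **Inputs from the SAP.** Section 5: 26,300 women and 3% incidence, so D = 26,300 × 0.03 = 789 events; 80% power; p < 0.05, two-sided by section 7.3. Table 2: SD 0.36 for dietary group. Supplementary Figure 1: SD² = p(1 − p), so p = 0.153 vegetarian.

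**The plan's own figure.** Minimum detectable HR = exp[2.8016 / (0.36 × √789)] = 1.319, against 1.32 in Table 2. It reproduces. The standard error (SE) of the log HR is 1 / (0.36 × √789) = 0.099 with full phase 2 response, and 1 / (0.36 × √394.5) = 0.140 if half respond (assumed).

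**Assumptions.** The SAP gives no mean follow-up, phase 2 response, early-event share, switching or supplement uptake. Let s be the share of events before phase 2. With 20 years of follow-up and cumulative hazard proportional to t^k, s = (4/20)^k: 20% for a flat hazard (k = 1), 4% for k = 2 and 2% for k = 2.43. Let q be the excess proportion of fractured non-vegetarians who are vegetarian by phase 2.

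**Repeat models, no true effect, vegetarian against all others.** Spurious HR = [1 + s·q·(1 − p)/p] / (1 − s·q):

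| s (events of 789) | q = 1% | q = 10% | q = 25% |
|---|---|---|---|
| 2% (16) | 1.001 | 1.013 | 1.033 |
| 5% (39) | 1.003 | 1.033 | 1.083 |
| 10% (79) | 1.007 | 1.066 | 1.168 |
| 20% (158) | 1.013 | 1.133 | 1.344 |

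Top cell: s·q = 0.05, so (1 + 0.05 × 0.847/0.153) / 0.95 = 1.344. Its log is 0.296, which is 3.0 SE with full response and 2.1 SE with 50% response. Nine of the 12 cells are below 1 SE with full response, and ten with 50%.

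Variations:
- Switching out of the vegetarian group gives 0.94–1.00.
- If women with an early fracture return phase 2 half as often, s = 20% becomes 0.10 / (0.10 + 0.80) = 11.1%, and the range is 1.001–1.187.
- Against regular meat-eaters, the planned reference (assumed 40–60% of the cohort, switching only from that group), the range is 1.001–1.26.

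A null simulation of 6 million women agrees. The ratio of the HR with the clock at entry to the HR with delayed entry is 1.351 for s = 20%, q = 25%, and 1.036 for s = 5%, q = 10%. Delayed entry itself gives HRs of 0.984–1.010, and dropping first-five-year cases 0.984–1.008 (Monte Carlo SE about 0.007).

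**Supplement strata, no true effect.** Let b be supplement use otherwise and u use after an early fracture, with subscript 1 for vegetarians and 0 for others. The spurious HR among users is {[(1 − s)b₁ + s·u₁]/b₁} / {[(1 − s)b₀ + s·u₀]/b₀}. Among non-users, replace b by 1 − b and u by 1 − u. The false interaction is the ratio of the two.

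- b = 25% in both, u = 60% vs 50%. At s = 2%: (0.257/0.255) / (0.743/0.745) = 1.01. At s = 20%: (0.32/0.30) / (0.68/0.70) = 1.10.
- b = 35% vs 20%, u = 60% in both. At s = 2%: 0.975/1.002 = 0.97. At s = 20%: (1.143/1.400) / (0.923/0.900) = 0.80.
- b and u each equal across groups: 1.00.

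**Cost of delayed entry.** With full response and 2%, 5%, 10% or 20% of events removed, the minimum detectable HR moves from 1.319 to 1.323, 1.329, 1.339 or 1.363. With 50% response it moves from 1.480 to 1.486–1.550.

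**The case against.** The strongest reply is that the SAP is silent here rather than wrong. It never defines study entry, section 2.1 speaks of recruitment instead, and section 7.3 does not say that the repeat models keep the baseline clock. An analyst might start follow-up at phase 2 without being told. That is possible, but nothing in the text gives study entry that meaning, and section 4 offers no second rule. The literal reading is the likelier one, and the choice should not stay open until the data are seen.

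Second, the five-year exclusion spans the whole gap before phase 2 and removes the bias in the simulation. This largely stands. What is missing is the link: the check is listed on its own, and nothing says that the phase 2 models will be run with it or read in that form.

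Third, the repeat models may never be run, since they depend on substantial change and adequate power. That is right for the repeat models. The supplement strata carry no such condition.

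Fourth, every input to the size is assumed. This stands in full. A reader might infer from 1.344 that the bias can mimic an effect of detectable size (1.32 in Table 2). That cell needs a flat fracture hazard over 20 years and a quarter of fractured non-vegetarians becoming vegetarian. The SAP supports neither.

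A reader might also infer that the supplement strata are safe if uptake after fracture is the same in every diet group. The second strata example shows otherwise: equal uptake protects only if use is otherwise equal too.

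**Conclusion.** The concern holds in a limited form. As written, models using phase 2 diet or supplement data count fractures that came before the exposure or stratum was recorded, and nothing in sections 7.2 or 7.3 prevents it. A reader might infer that the main results are at risk. They are not: the primary models use baseline diet and exclude fractures up to recruitment, so exposure precedes event. The harm is confined to conditional sensitivity models and exploratory subgroups.

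The size is open. Under the assumptions above, the repeat models carry a spurious HR of 1.001–1.344, mostly below one SE, and the strata examples a false interaction ratio of 1.01–1.10 or 0.97–0.80. No figure is derived for food or nutrient exposures. The defect should be corrected because the correction is cheap, not because the bias is known to be large.

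**What to change.** State in sections 7.2 and 7.3 that every model using phase 2 diet or supplement data starts risk time at the phase 2 questionnaire date (delayed entry) and excludes women with a hip fracture on or before that date. State also that the power condition for the repeat models is judged on events after that date.

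This takes two or three sentences, plus an entry date and a fracture-date exclusion in the code. The price is the early events: the minimum detectable HR for dietary group goes from 1.32 to at most 1.36 with full response, or from 1.48 to at most 1.55 with an assumed 50% response. Non-response therefore costs more than the fix.

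Whether the repeat models also use covariates measured at phase 2 is optional and not part of this change. In the supplement strata, where baseline diet remains the exposure, phase 2 covariates could be consequences of that diet, and section 7.1.1 requires confounders to be "not caused by the exposure".

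### Sections 2.1 and 8 of the SAP handle missing covariates by different rules, and under section 8 the models set side by side can rest on different women

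*SAP*

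**What the plan says.** **Exclusion criteria (SAP section 2.1).** The list opens with "Participants will be excluded from analyses for any of the following reasons". One reason is "Unreliable or missing nutrient or covariate data", and its only example is a share of missing food frequencies. The other reasons apply to the whole cohort: residence outside England, failed record linkage, and hip fracture or osteoporosis at or before recruitment.

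**Missing data (SAP section 8).** Three rules are given:
- for the FFQ: "Participants with missing data for an FFQ item will be considered non-consumers";
- for everything else: "Participants will be excluded from each specific analysis if they have missing data for any other variable required in that analysis";
- on imputation: "Techniques to impute missing dietary or covariate data will not be performed".

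**Models shown together.** Section 7.1.1 states: "For all primary analyses, we will present age-adjusted, minimally adjusted, and fully adjusted models". Section 7.3 adds: "Models will be presented with and without adjustment for BMI". It also plans to explore mediation by adding candidate covariates to the adjusted models one at a time.

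**Sample size (SAP section 5).** The calculation takes 26,300 women after the exclusion criteria and a 3% probability of hip fracture. It gives a minimum detectable hazard ratio of 1.32 for dietary group.

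**The concern.** Take a woman whose only gap is smoking status. Under section 2.1 as worded she leaves the analyses. Under section 8 she stays in every model that does not use smoking, including the age-adjusted one. If section 2.1 were applied to every covariate, section 8 would have almost nothing left to do. Two analysts following this SAP could therefore build different datasets.

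The second issue arises if section 8 is the operating rule. Readers normally take the movement from the age-adjusted to the minimally adjusted estimate as a sign of confounding, and the movement with and without BMI as a sign of the role of BMI. The mediator exercise in section 7.3 depends on such a movement by design. If the women change along with the covariates, the movement combines adjustment with selection, and the reader cannot separate them. The SAP takes selection seriously elsewhere: section 7.1.1 adjusts for chronic disease and earlier fractures rather than excluding those women.

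**Working it through.** **1. The plan's own figure.** Inputs from section 5 and Table 2: N = 26,300, event probability 3%, SD of dietary group 0.36, 80% power. Section 7.3 gives two-sided 0.05.

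Events D = 26,300 × 0.03 = 789.

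Minimum detectable HR = exp[(z0.975 + z0.80) / (SD × √D)] = exp[2.8016 / (0.36 × √789)] = 1.319.

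This reproduces the stated 1.32.

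**2. Who is in each model under section 8.**

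| Model | Variables needed | Effect on the sample |
|---|---|---|
| Age-adjusted | age | nearly everyone kept |
| Minimally adjusted | the likely confounders, BMI among them | drops women missing any of them |
| Same, without BMI | the same less BMI | regains women missing only BMI |
| Fully adjusted | adds competing exposures | few or none lost where these come from the FFQ, since a missing item counts as non-consumption |
| Mediator models | adds one covariate | may drop more if the covariate is not from the FFQ |

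**3. Possible size.** Section 7.1.1 names 13 likely confounders (counting BMI, or height and weight, as one). Age is needed in every model, so 12 can cause a loss relative to the age-adjusted model. The SAP gives no missingness rates. Assume that each of the 12 is missing independently in a share m of women:

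share kept = (1 − m)^12; without BMI, (1 − m)^11.

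| m (assumed) | Share kept, all 12 | Women, if starting from 26,300 | Women in the model without BMI | Difference due to BMI |
|---|---|---|---|---|
| 1% | 0.886 | 23,312 | 23,547 | 235 |
| 2% | 0.785 | 20,638 | 21,059 | 421 |
| 5% | 0.540 | 14,211 | 14,959 | 748 |

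**4. Detectable hazard ratio, only if the 26,300 precedes these losses.** Replace 789 by 789 × share kept:

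- 1%: exp[2.8016 / (0.36 × √699.4)] = 1.34
- 2%: exp[2.8016 / (0.36 × √619.1)] = 1.37
- 5%: exp[2.8016 / (0.36 × √426.4)] = 1.46

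If the 26,300 is already net of missing covariates, the figure stays at 1.32.

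**The case against.** The best defence is that the two sections work in sequence. Section 2.1 does not say that women leave all analyses, and its only example is a screen for poor dietary data. Section 8 could then be the detailed rule for gaps that remain. This reading is reasonable, but the SAP does not state it and section 2.1 names covariate data explicitly. On this reading section 8 governs covariates, so the change of sample between models remains.

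Section 8 also leaves open what counts as one specific analysis. If it meant the whole set of models for one exposure, those models would share a sample and the second issue would disappear. Nothing in the SAP says so.

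The loss may also be smaller than illustrated. The confounder list is provisional until the causal diagrams are drawn. Women who skip one question often skip several, which breaks the independence assumption and reduces the loss. Supplementary Table 2 lists a missing option for education. If that is kept as a category, 11 covariates remain and the shares kept become 90%, 80% and 57%. These points stand: the size is unknown, and the 5% row is only an illustration.

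Finally, the SAP says only that the adjusted models and those with and without BMI will be presented. It states an interpretive purpose for the mediator models alone. That is fair, but models presented side by side will be compared.

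**Conclusion.** The conflict between sections 2.1 and 8 is in the current text and should be resolved. Under section 8 as written, three comparisons can mix adjustment with a change of women: age-adjusted against minimally adjusted, with against without BMI, and with against without a mediator from outside the FFQ. Under the assumptions above, the minimally adjusted model keeps about 89%, 78% or 54% of the women in the age-adjusted model. The true share cannot be found from the SAP.

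A reader might infer more than the document supports:

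- **That the power calculation is wrong.** Section 5 counts women after the exclusion criteria, and section 2.1 bears that heading and includes missing covariates. On the plain reading the 26,300 is net of those losses and 1.32 stands. The values 1.34, 1.37 and 1.46 apply only on the other reading.
- **That every further adjustment loses more women.** BMI is already among the likely confounders, so the model with BMI loses nobody beyond the minimally adjusted one. FFQ-based competing exposures lose few or none.
- **That the comparisons are worthless.** With little missingness, or missingness unrelated to the association between exposure and fracture, they remain informative. No primary estimate is shown to be biased.

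**What to change.** 1. State one rule. Limit the data-quality item in section 2.1 to unreliable dietary data, and let section 8 govern missing covariates.
2. For each exposure, fit the age-adjusted, minimally adjusted and fully adjusted models, and those with and without BMI, on one set: the women complete for all variables of the fully adjusted model, BMI included.
3. For each mediator model, refit the reference adjusted model on the women complete for that mediator, and compare the two there. Do not restrict the primary models to women complete on every mediator, because that would cost them precision for the sake of exploratory work.
4. Report N and events for every model.
5. State in section 5 which set of women the 26,300 describes.

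The cost is a few sentences, one sample flag per exposure and some refits. The age-adjusted models and those without BMI will use somewhat fewer women than section 8 now allows. A common set makes the models comparable with each other. It does not remove selection that comes from analysing complete cases only.
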